9.1.3. Sensitivity Analyses

Sensitivity analyses for the primary estimand will be conducted under the hypothetical strategy framework using the ITT Analysis Set. These sensitivity analyses will only be needed where the JZP385 group demonstrates a statistically significant improvement over the placebo group, based on the criteria outlined in Section 7.3.

[figure not shown]
Under the hypothetical strategy, the MAR assumption is being followed for the primary analysis, which supports the justification for using an MMRM model. This is supplemented by the possibility of data being MNAR, assessed under the sensitivity and supplemental analyses.

9.1.3.1. Pattern Mixture Model

A control-based Pattern Mixture Model will be used to explore the possibility of data being MNAR for participants who discontinued early from study due to either lack of efficacy or an adverse event. For participants who early discontinued due to other reasons, missing data will be imputed assuming MAR. Control-based Imputation (CBI) method assumes a mean and variance based on the control group for participants who withdrew from the JZP385 group at the time of withdrawal to the imputed timepoint, with the observed values prior to withdrawal still considered, thus a slow decay back toward the control group mean eventually. (Carpenter JR, 2013) This method assumes that from withdrawal onwards, participants in the active treatment group will progress back to the participants in the control group.

Figure 2 illustrates MAR estimates versus the estimates derived from CBI (assuming study participants withdraw at Visit 2 and a lower response indicates improvement).

Figure 2 MAR vs CBI

The control-based imputation will be implemented through steps below:

Treatment dropouts and missing observations at Weeks 4, 8 and 12 will be imputed using the multiple imputation method. MI procedure in SAS will be used to impute the missing TETRAS composite outcome score at the missed visit to create 20 complete datasets.

The missing data pattern will be checked. If any non-monotone missing data pattern is observed, 2 separate steps will be followed to complete the imputation, starting with Step 1. If a monotone missing data pattern is observed, skip to Step 2 directly (set imputation number to 20 instead).

Step 1: the Markov Chain Monte Carlo (MCMC) method will be used with a single chain to impute TETRAS composite outcome score by treatment, baseline stratification group as well as baseline TETRAS composite outcome score to create 20 imputed datasets with monotone missing patterns. Set the seed as 8715942. Imputed scores should be rounded to nearest integer, with the minimum and maximum possible score set to 0 and 42 respectively, which corresponds to the range of possible TETRAS composite outcome score.

Step 2: the predictive mean matching (PMM) method will be used to impute the remaining missing scores for the 20 imputed datasets with monotone missing patterns. The imputation procedure will use monotone statement to create 1 compete dataset for each of the monotone datasets from Step 1, with model variables to include treatment, baseline stratification group, as well as TETRAS composite outcome score at scheduled visits from Baseline to Weeks 4, 8 and 12. Set the seed as 4985135 and number of closest observations to 2.

For participants who discontinued the study early due to either lack of efficacy or an adverse event, the post-discontinuation values imputed through Steps 1 and 2 will be set to missing and rederived using CBI method (MNAR).

The imputed datasets with a mixture of MAR and MNAR imputations will be analyzed separately using the MMRM model specified in 9.1.2, then final inference will be pooled using the MIANALYZE procedure and reported.

9.1.3.2. Tipping Point Analyses

Tipping point analyses will be used to investigate the robustness of the primary analysis method. The delta adjusting approach (O'Kelly & Ratitch, 2014) will be used to find the tipping point, at which JZP385 is no longer statistically significant. This analysis will only be performed where a JZP385 treatment group shows a statistically significant improvement against placebo, based on the criteria outlined in Section 7.4.

The marginal delta approach will be used for tipping point analyses by following Steps 1 and 2 specified above (Section 9.1.3.1) and then followed by:

Step 3: For participants in a JZP385 treatment group, make the imputed value worse by an increment of delta, with the initial delta value set at 0, which is equivalent to the MAR estimate, and increases delta value by 10% of the maximum observed treatment difference among all dose groups at each time, until the tipping point is detected.

The primary analysis will be reperformed, using the MMRM model specified in Section 9.1.2, for each imputed dataset, at each delta. The results from the datasets, at each delta, will be pooled, using the MIANALYZE procedure.

The delta identified at which the results are no longer statistically significant will be the tipping point. After the tipping point is determined, clinical judgement will be applied to the plausibility of the assumptions underlying this tipping point.

9.1.4. Completers Analysis (Data as Observed)

The primary analysis in Section 9.1.2 will only include the participants who have the TETRAS composite outcome score at Weeks 4, 8 and 12. This constitutes a Completers Analysis. Normality assumptions will not be reassessed. The corresponding parametric or nonparametric analysis will be used from the primary analysis.

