- ^d If participant discontinues study intervention and requires an E/D Visit, the Safety FU should be 2 weeks after the E/D visit.
- ^e Clinic visits at Week 1, Week 4, Week 8, E/D, and EoS/Safety FU may be conducted remotely, if required due to the COVID-19 pandemic, and with approval from the sponsor's medical monitor. The TETRAS-PS will not be performed at remote visits, and PK samples may not be collected.
- f Phone contacts at Weeks 2 to 3, Weeks 5 to 7 and Weeks 9 to 11 may be converted to clinic visits if required due to local regulations or local requirements. If performed in-clinic, dispensing of study intervention may occur and urine pregnancy testing should be completed for WOCBP.

CONFIDENTIAL Page 26 of 109

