For sensitivity analyses, a control-based Pattern Mixture Model (PMM) will be used to explore the possibility of data being missing not at random (MNAR). A supplementary analysis will be conducted with only those participants who have Week 12 TETRAS composite outcome scores. Additional details on sensitivity and supplementary analyses will be provided in the SAP.

Subgroup analyses by randomization stratum, sex, age, and region will be conducted as applicable. Further details will be provided in the SAP.

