9.4.3. Secondary Estimands and Endpoints

9.4.3.1. Key Secondary Estimand

The attributes of the key secondary estimand are listed below:

- Treatment: 10, 20, and 30 mg/day JZP385 and placebo.
- Population: Adults with moderate to severe ET.
- Variable: Proportion of participants who improved (≥ 1 point improvement) from Baseline to Week 12 on the CGI-S.

• Intercurrent Events:

- Discontinuation of study intervention due to an AE, for lack of efficacy, or any other reason. Participants who experience this type of intercurrent event will be addressed by hypothetical strategy.
- Any change to concomitant antitremor medication use after the initiation of study intervention (refer to Section 9.4.1.2). Participants who experience this type of intercurrent event will be addressed by treatment policy.
- Summary: Difference in the proportion of participants who improved (≥ 1 point improvement) from Baseline to Week 12 on the CGI-S between each dose of JZP385 and placebo.

The main estimator will be analyzed using the CMH test adjusting for the stratification factors at randomization (baseline TETRAS composite outcome score [≤ 17 or > 17] and the use of concomitant antitremor medication [Yes or No]). The 2-sided p-values from the CMH test, the adjusted treatment difference in proportion using the weighted average of the treatment differences across the strata with the CMH weights, and the associated 2-sided 95% CIs using a normal approximation to the weighted average will be provided.

For the intercurrent event of discontinuation of study intervention due to an AE, for lack of efficacy, or any other reason, under the hypothetical strategy, the primary analysis will adopt a 2-step multiple imputation approach, with MCMC to impute non-monotone intermittent missing followed by a predictive mean matching method to impute the rest monotone missing outcomes.

Sensitivity analysis will be conducted through the tipping point analysis, with further details provided in the SAP.

Supplementary analyses will be performed using the Non-responder Imputation (NRI) method as well as completers analysis with only participants who have Week 12 CGI-S assessment.

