9.2.4. Completers Analysis (Data as Observed)

The primary analysis in Section 9.2.2 will be conducted to only include the participants who have the CGI-S at Week 12. This constitutes a Completers Analysis. The corresponding CMH analysis will be used from the primary analysis.

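### The SAP's completers analysis of the TETRAS composite requires scores at Weeks 4, 8 and 12, where the protocol requires only Week 12, and the change is not declared

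*SAP*

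**What the plan says.** The two documents describe the population of this supplementary analysis differently.

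- Protocol 9.4.2: "A supplementary analysis will be conducted with only those participants who have Week 12 TETRAS composite outcome scores". It leaves further details of supplementary analyses to the SAP.
- SAP 9.1.4: the analysis "will only include the participants who have the TETRAS composite outcome score at Weeks 4, 8 and 12".

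For the key secondary endpoint they agree. Protocol 9.4.3.1 plans a "completers analysis with only participants who have Week 12 CGI-S assessment", and SAP 9.2.4 says that its analysis "will be conducted to only include the participants who have the CGI-S at Week 12".

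SAP Section 3 states that the SAP is based on Protocol Amendment 04, so both texts are current. SAP 7.6, which records changes to planned analyses, lists three: the item-level imputation rule, the move from mITT to ITT, and the removal of presyncope from the events of special interest. The completers population is not among them.

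Two further provisions bear on who has an interim score. A footnote to the Schedule of Activities (Protocol 1.3) says: "Clinic visits at Week 1, Week 4, Week 8, E/D, and EoS/Safety FU may be conducted remotely", but only where the pandemic makes it necessary and the medical monitor approves. Week 12 is not on that list. The same footnote adds: "The TETRAS-PS will not be performed at remote visits, and PK samples may not be collected". SAP 7.2.5 then gives no composite for a visit at which two or more of the three contributing performance items are missing.

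**The concern.** A supplementary analysis of this kind should show the Week 12 result in those who reached Week 12 and were assessed. Under the SAP rule, some of those people are removed because of a gap at Week 4 or Week 8. Their Week 12 outcome was observed, it is the outcome that the estimand concerns, and the MMRM in SAP 9.1.2 can use it without complete interim visits.

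Three things are at stake, all modest. The analysis loses precision. The included set is selected on interim attendance as well as on reaching Week 12. And two analyses with the same title in the SAP (9.1.4 and 9.2.4) follow different inclusion rules with no reason given, so a reader of the study report who sets them side by side could be misled.

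**Working it through.** **Plan's own figure.** SAP 5.3 gives 80 evaluable participants per group, a difference of 3.1, SD 6.0 and two-sided 0.05, for 90% power. The standard error of a difference is 6.0 × √(2/80) = 0.949. The noncentral t calculation with 158 degrees of freedom gives 90.1%, so the figure reproduces. A group of 80 is used below as the number with a Week 12 score.

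**How an interim composite goes missing.**

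1. A Week 4 or Week 8 visit is held remotely under the footnote in Protocol 1.3, so the performance subscale is not done.
2. Item 6 (left and right hand) and item 7 are then absent, which is 3 of 3 performance items.
3. SAP 7.2.5 tolerates one missing performance item. With three missing, no composite is calculated.
4. SAP 7.2.3 leaves the analysis visit missing unless another assessment falls in its window (days 2–42 for Week 4, days 43–70 for Week 8).
5. SAP 9.1.4 then excludes the participant, even with a valid Week 12 score.

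Step 3 comes from the SAP's revised rule. Protocol 9.4.1.4 allowed up to 3 of the 14 items to be imputed from the rest, so a remote visit with all 11 ADL items could still have produced a composite. SAP 7.6 declares that revision, but not its interaction with the completers rule. An interim visit missed altogether leads to the same exclusion.

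**Size.** The documents give no interim missing rate. Let q be the assumed share of participants with a Week 12 score who lack a composite at each interim visit.

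- If the same people miss both visits, the share retained is 1 − q.
- If the gaps are independent, the share retained is (1 − q)².
- The standard error grows by 1/√(share retained).

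| q (assumed) | Gaps | Dropped | Left of 80 | SE factor |
|---|---|---|---|---|
| 5% | same people | 5% | 76.0 | 1/√0.95 = 1.026 |
| 5% | independent | 1 − 0.95² = 9.75% | 72.2 | 1/0.95 = 1.053 |
| 10% | same people | 10% | 72.0 | 1/√0.90 = 1.054 |
| 10% | independent | 1 − 0.90² = 19% | 64.8 | 1/0.90 = 1.111 |

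If nobody missed both visits, the loss would be 2q, that is 10% and 20%, which is little more than under independence. With the protocol's rule, all 80 stay in.

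**The case against.** The best defence is that the SAP rule is a recognisable complete-data version of the primary model. That model uses Weeks 4, 8 and 12, so a data-as-observed analysis might reasonably ask for all three. CGI-S is tested at Week 12 alone by a CMH test, so the parallel with SAP 9.2.4 is not exact, and the two sets could differ even under a common rule because a composite and a CGI-S rating can be missing separately. This stands as an argument that the choice is defensible. It does not explain why a population that the protocol states explicitly was replaced without an entry in SAP 7.6. Leaving details to the SAP does not clearly extend to a different population.

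It also stands that remote visits are limited to pandemic need with approval, and that the wide windows admit unscheduled in-clinic assessments. Not every remote or missed visit leads to exclusion. The relief is partial, because between the scheduled clinic visits the schedule has phone contacts and no planned performance assessment.

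Three stronger readings are tempting, and the documents do not support them:

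- A reader might infer from the wording of SAP 9.1.4 that the primary analysis itself is restricted to people with all three scores. SAP 9.1.2 and Section 9 place the primary MMRM in the ITT set, and 9.1.4 is headed as a completers analysis.
- A reader might infer that the SAP breaks a protocol definition of completers for this endpoint. Protocol 9.4.2 does not use that term here, and Protocol 4.4 defines completing the study by its last scheduled procedure. The conflict is only over which scores are required.
- A reader might infer a biased treatment comparison. Any set chosen by having a Week 12 score is already selected after randomisation, and nothing in the documents shows that the added interim condition acts differently by arm.

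**Conclusion.** The point holds as an undeclared mismatch between Protocol 9.4.2 and SAP 9.1.4, with a mechanism in the documents by which observed Week 12 outcomes are discarded. On the assumed rates of 5% and 10% per interim visit, between 5% and 19% of participants with a Week 12 score would leave the analysis and its standard error would rise by roughly 3% to 11%. These figures depend on the assumed rates, on how far the two gaps overlap, and on no other in-window assessment filling them. The actual loss could be smaller and cannot be computed from the documents. The analysis lies outside the fixed testing sequence in SAP 7.4, so the primary MMRM and the family-wise error rate are untouched. The correction is worth making because it is nearly free.

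**What to change.** In SAP 9.1.4, state that the MMRM of Section 9.1.2 will be repeated in participants who have a Week 12 TETRAS composite score, using all their available Week 4 and Week 8 data. This restores the population in Protocol 9.4.2 and parallels SAP 9.2.4. Saying that the model is repeated also removes the impression that the primary analysis is being narrowed.

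Do not add a condition that the Week 12 score was obtained on study intervention. Neither Protocol 9.4.2 nor SAP 9.2.4 contains one, and it would be a further change needing its own definition.

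If the sponsor prefers the three-visit rule, the alternative is to keep it, list it in SAP 7.6 with a reason, and report how many participants with a Week 12 score it removes in each arm.

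The preferred change costs one sentence in the SAP and a simpler selection rule in the program. It needs no new data.

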9.1.5. Subgroup Analyses

Subgroup analyses for groups specified in Section 7.5 will be performed for the primary efficacy estimand using the ITT Analysis Set. The primary analysis in Section 9.1.2 will be used for the subgroup analyses. However, the randomization stratification factor will be removed from the model for the analysis by subgroups of participants by randomization strata. The corresponding parametric analysis used for the overall sample will be applied to each subgroup. A forest plot summarizing the treatment difference and 95% CI will be provided for each subgroup with sufficient sample size.

9.2. Secondary Efficacy Estimand, Endpoints and Analyses

9.2.1. Key Secondary Efficacy Estimand

The attributes of the key secondary estimand are listed in Section 4.1.2.

The CGI-S is a 5-point Likert-type ordinal scale. The responses to this investigator-completed scale range from 1 to 5 and correspond to the following categories:

- No limitations (1)
- Mild (2)

- Moderate (3)
- Marked (4)
- Severe (5)

For analysis purposes, CGI-S will be treated as a dichotomous variable where a response is defined as $a \ge 1$ -point decrease (improvement) from Baseline to Weeks 4, 8 and 12. For the estimator, the proportion of participants who have achieved the response at Week 12 will be compared between JZP385 and placebo groups.

9.2.2. Primary Analysis

The main estimator of the key secondary estimands will be analyzed using the CMH test adjusting for the stratification factor at randomization (Baseline TETRAS composite score: ≤ 17 or > 17 and antitremor medication use at Baseline: Yes or No). Number of responders in each group, proportion as well as 95% CI (Wilson score method) will be reported at Week 12. The 2-sided p-values from the CMH test, the unadjusted treatment difference as well as the adjusted treatment difference in proportion using the weighted average of the treatment differences across strata with CMH weights, and the associated 2-sided 95% CI using a normal approximation to the weighted average will be derived and reported at Week 12.

Treatment dropouts and missing observations for the main analytic approach will be handled through multiple imputation (MI), a method that relies on observed values from similar participants who remained in the study to bridge information to deduce missing observations. Missing values at Weeks 4, 8 and 12 for CGI-S will be imputed using the MI method. The MI procedure in SAS will be used to impute a missing CGI-S score at the scheduled visit to create 20 complete datasets.

The missing data pattern will be checked at Baseline, Weeks 4, 8 and 12. If any non-monotone missing pattern is observed, 2 separate steps will be followed to complete the imputation, starting with Step 1. If a monotone missing pattern is observed, skip to Step 2 (setting imputation number to 20)

Step 1: the Markov Chain Monte Carlo (MCMC) method will be used with a single chain to impute missing CGI-S scores by treatment, baseline stratification group as well as baseline CGI-S score to create 20 imputed datasets with monotone missing patterns. Set the seed as 8715942. Imputed scores should be rounded to nearest integer, set minimum and maximum possible score to 1 and 5 respectively, which corresponds to the range of CGI-S.

Step 2: the predictive mean matching (PMM) method will be used to impute the remaining missing CGI-S scores for the 20 imputed datasets with monotone missing patterns. The imputation procedure will use monotone statement to create 1 compete dataset for each of the monotone datasets from Step 1, with model variables include treatment, baseline stratification group, as well as CGI-S score at scheduled visits from Baseline to Weeks 4, 8 and 12. Set the seed as 4985135 and number of closest observations to 2.

The imputed datasets will be analyzed using CMH test, and the final inference will be pooled using SAS procedure MIANALYZE.

The following is an example SAS code for CMH analysis:

PROC SORT DATA = CGIS;

```
Jazz Pharmaceuticals
Statistical Analysis Plan - Protocol JZP385-201
BY IMPUTESEO VISIT TRT STRATUM DECENDING RESPONSE:
RUN;
PROC SQL;
CREATE TABLE ADDIN AS
SELECT DISTINCT IMPUTESEQ, VISIT, TRT, STRATUM, 1 AS RESPONSE
FROM CGIS;
QUIT;
DATA CMH;
MERGE CGIS (IN=A) ADDIN (IN=B);
BY IMPUTESEQ VISIT TRT STRATUM DECENDING RESPONSE;
IF B AND NOT A THEN WGT = 0;
ELSE WGT = 1;
RUN:
*Adjusted (Stratified) Difference and CMH TEST;
PROC FREQ DATA=CMH;
BY IMPUTESEO AVISITN:
TABLES STRATUM*TRT*RESPONSE/RISKDIFF (COMMON CL=(NEWCOMBE)) CMH;
WEIGHT WGT/ZEROS;
RUN;
*Unadjusted (Unstratified) Difference;
```

PROC FREQ DATA=CMH;
BY IMPUTESEQ AVISITN;
TABLES TRT*RESPONSE/RISKDIFF CMH;

WEIGHT WGT/ZEROS;

RUN;

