5.1. Inclusion Criteria

Participants are eligible to be included in the study only if all of the following criteria apply:

Age

1. Participant must be 18 to 80 years of age inclusive, at the time of signing the informed consent.

Type of Participant and Disease Characteristics

- 2. Participants who are diagnosed with ET (including ET plus) according to the MDS Consensus Statement on the Classification of Tremors from the Task Force on Tremor of the International Parkinson's and Movement Disorder Society (Bhatia, 2018) and centrally reviewed by an Eligibility Adjudication Committee (EAC; see Section 10.1.5).
- 3. Participants have moderate to severe disability associated with tremor at both the Screening and Baseline visits, as determined by all of the following:
 - a. Score of \geq 22 on the TETRAS-ADL subscale; and
 - b. *Note*: This criterion has been removed in Amendment 3.
 - c. CGI-S rating of at least moderate for participants' ability to function.

Note: Participants who need washout of a medication(s) that could impact their tremor assessment (eg, medications that produce tremor **or** that treat tremor but are prohibited because of potential PK drug-drug interactions with study intervention [such as primidone]) at Screening Visit 1 must return to the clinic for a second Screening Visit (Screening Visit 2). For these participants, the Screening TETRAS-ADL subscale and CGI-S assessments that will be used to determine eligibility will be performed at Screening Visit 2, after participants have washed out their medication.

Sex and Contraceptive/Barrier Requirements

- 4. Participant is male or female.
 - a. Male participants:

Male participants are eligible to participate if they agree to the following during the study intervention period and for at least 30 days after the last dose of study intervention:

• Refrain from donating sperm.

PLUS, either:

• Be abstinent from heterosexual intercourse as their preferred and usual lifestyle (abstinent on a long-term and persistent basis) and agree to remain abstinent.

OR

- Must agree to use contraception/barrier as detailed below:
 - Agree to use a male condom with female partner use of an additional highly effective contraceptive method with a failure rate of < 1% per year (as described in Appendix 5) when having sexual intercourse with a woman of childbearing potential (WOCBP) who is not currently pregnant.

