5.3. Power and Sample Size Calculations

A sample size of 80 evaluable participants per treatment group will provide 90% power to detect a difference of 3.1 points for the change from Baseline to Week 12 on the TETRAS composite outcome between JZP385 and placebo, with a common SD of 6.0 points. This sample size will also provide 91.7% power to detect a 26% between-treatment (assuming JZP385 at 66% versus placebo at 40%) difference in proportion of participants who improved by at least 1 point on the CGI-S from Baseline to Week 12. Assuming a 20% dropout rate, a total of 400 participants (100 participants per treatment group) will be randomized. The sample size calculation for the TETRAS composite outcome score is based on t-test and the CGI-S sample size calculation is based on chi-square test, both tests are 2-sided at the significance level of 0.05.

For the TETRAS composite outcome, at least 80% power is still achieved if there is a reduction of 0.4 points from the assumption in the difference in mean change from baseline (assuming a constant common standard deviation) or an increase in common standard deviation by 1 point, (assuming a constant difference in means). For the key secondary endpoint, at least 80% power is still achieved with comparable shifts in the assumptions.

The assumptions for these sample sizes were supported by the results from the Phase 2 study in Essential Tremor (Study CX-8998-CLN2-001 [T-CALM]), where the TETRAS ADL and PS were assessed. Using the same derived TETRAS composite outcome score, as defined in this SAP, and assessing the change from baseline to Day 28 in T-CALM, there was a difference in means between JZP385 and placebo of 3.04 and a difference in LS Means of 3.27. The standard deviation for the change from baseline was 5.86 in JZP385 and 5.47 in placebo. It is hypothesized that the treatment improvement will remain consistent over the longer study duration of JZP385-201, with a small increase in variability, thus supporting the above assumptions.

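### The key secondary CGI-S responder test adjusts for the two randomisation factors but not for baseline CGI-S; adding it would bring a modest gain in efficiency and robustness, though the planned test is valid

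*SAP*

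**What the plan says.** Response on the key secondary endpoint is a fall of at least 1 point on the 5-point CGI-S from the participant's own baseline to Week 12 (SAP 4.2.2 and 9.2.1). Protocol 5.1 requires a "CGI-S rating of at least moderate" at both Screening and Baseline, so eligible participants start at 3, 4 or 5.

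On the test, SAP 9.2.2 states: "The main estimator of the key secondary estimands will be analyzed using the CMH test adjusting for the stratification factor at randomization". It names the two factors, which make 2 × 2 = 4 strata. Protocol 9.4.3.1 specifies the same CMH test, with a CMH-weighted risk difference and a normal-approximation interval. The non-responder, tipping-point and completers analyses (SAP 9.2.3 and 9.2.4) do not add baseline CGI-S, and it is not a listed subgroup (SAP 7.5).

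Baseline CGI-S does enter elsewhere. Imputation Step 1 uses it, and Step 2 is specified "with model variables include treatment, baseline stratification group, as well as CGI-S score at scheduled visits from Baseline to Weeks 4, 8 and 12". SAP 8.3 summarises it by arm.

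Other endpoints adjust for their own baseline as well as the stratum: the primary MMRM (SAP 9.1.2), QUEST (9.2.6.3) and ETEA (9.2.6.4).

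**The concern.** The starting category probably influences who responds. A participant rated 5 cannot be rated worse, so rating noise can move that participant only downwards; a participant rated 3 can move either way. If baseline CGI-S is prognostic, an analysis that leaves it out has a larger standard error than necessary. An arm that happens to start with fewer marked or severe participants is then compared on unequal terms. The TETRAS stratum balances CGI-S only indirectly.

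The position of the endpoint raises the stakes. CGI-S at 30 mg is the second of six sequential tests (SAP 7.4). If it fails, neither the 20 mg nor the 10 mg comparison is formally tested, on the TETRAS composite or on CGI-S.

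**Working it through.** **1. The plan's own figure.** SAP 5.3 rests on "A sample size of 80 evaluable participants per treatment group", and this is said to "also provide 91.7% power to detect a 26% between-treatment" difference, "assuming JZP385 at 66% versus placebo at 40" per cent. It adds that "the CGI-S sample size calculation is based on chi-square test" and that "both tests are 2-sided at the significance level of 0.05".

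- Pooled rate: (0.66 + 0.40)/2 = 0.53.
- SE under the null: √(2 × 0.53 × 0.47/80) = 0.0789.
- SE under the alternative: √((0.66 × 0.34 + 0.40 × 0.60)/80) = 0.0762.
- Power = Φ((0.26 − 1.96 × 0.0789)/0.0762) = Φ(1.38) = 91.7%.

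The figure reproduces (91.66%). It uses no covariates, so the sample size does not depend on any adjustment gain.

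**2. Validity of the planned test.** In simulation under no treatment effect, the four-stratum CMH rejected in 4.9% to 5.1% of trials, whether or not baseline CGI-S was prognostic.

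**3. Power with baseline CGI-S added.** The following are assumptions, because the documents give none of them:
- baseline CGI-S 3/4/5 in 50/35/15%;
- TETRAS composite > 17 in 40/65/85% at those levels;
- antitremor use in 50%;
- complete data, 80 per arm, overall rates 66% and 40%;
- the odds of response multiplied by a constant ratio (OR) per CGI-S level. At OR 2 the placebo response is 29/45/63% by level; at OR 3 it is 24/49/74%.

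The logistic estimator fits treatment, both stratification factors and baseline CGI-S as main effects. It predicts each participant's response under active and under placebo, and averages the differences:

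RD = (1/N) Σ [p̂ᵢ(active) − p̂ᵢ(placebo)].

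Power (%), without → with baseline CGI-S:

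| OR per level | CMH, 4 → 12 strata | Linear main effects, robust SE | CMH → logistic RD, set A | CMH → logistic RD, set B |
|---|---|---|---|---|
| 1 | 91.0 → 89.6 | 90.4 → 90.0 | 91.6 → 91.9 | 91.0 → 91.4 |
| 1.5 | 91.1 → 90.3 | 90.7 → 90.7 | 90.4 → 91.3 | not run |
| 2 | 91.4 → 91.5 | 91.1 → 92.2 | 91.6 → 93.6 | 90.8 → 92.9 |
| 3 | 91.4 → 93.2 | 91.3 → 93.7 | 91.3 → 94.3 | 90.8 → 94.4 |

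The CMH column used 20,000 trials per row, the linear column 8,000 and set A 4,000. Sets A and B are separate runs of the same comparison. With 4,000 trials the Monte Carlo SE at 91.4% is √(0.914 × 0.086/4,000) = 0.44 points.

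Main-effects adjustment therefore changes power by about 0 to +3.5 points. Crossing baseline CGI-S with the existing strata gives 12 cells of about 160/12 = 13 participants and loses 91.0 − 89.6 = 1.4 points when there is no gradient.

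For a smaller effect, 60% versus 40%, the logistic RD against the CMH gave 74.6% versus 71.3% (OR 2) and 78.5% versus 72.8% (OR 3).

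**4. Chance imbalance.** If half the participants are marked or severe, the SD of the between-arm difference in that share is √(2 × 0.25/80) = 0.079. A gap of 10 points or more in either direction has probability 2 × (1 − Φ(0.10/0.079)) ≈ 21% per comparison at 80 per arm, and about 16% at 100. In the roughly 10% of trials where the active arm is short of marked or severe participants by that much, power was:

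| Scenario | CMH | Logistic RD |
|---|---|---|
| 66% v 40%, OR 2 | 84.1% | 94.0% |
| 66% v 40%, OR 3 | 82.5% | 94.9% |
| 60% v 40%, OR 3 | 55% | 80% |

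**5. Is a gradient plausible?** A noisy five-category rating was simulated with entry at 3 or more and no true change, using assumed cut-points. Apparent placebo response at baseline 3/4/5 was 23/50/65%, 19/43/53% and 11/31/34% at reliabilities of 0.60, 0.75 and 0.90. The odds ratio was above 3 from level 3 to 4, and about 1.1 to 1.9 from 4 to 5. This illustrates a mechanism; it is not trial evidence.

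**6. Size of the adjusted test.** With an uncorrected SE, null rejection was 5.0–5.7% in set A (CMH 4.5–5.3%) and 5.5–6.1% in set B (CMH 4.6–5.7%). Part of the logistic gain may come from this slightly small SE. The linear column, which corrects for leverage, shows smaller gains.

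**The case against.** The planned analysis is an accepted one for a binary endpoint. It is pre-specified in both documents, adjusts for both randomisation factors, keeps its type I error and reaches its stated power unaided. All of that stands.

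Four stronger readings are tempting, and the documents support none of them:

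- A reader might infer that the plan ignores baseline CGI-S. It does not: baseline CGI-S defines response, informs both imputation steps and is tabulated by arm. It is absent only from the test.
- A reader might infer that baseline sets how far a participant can improve and so blocks some responses. Entry at 3 or above on a scale that runs down to 1 leaves everyone at least 2 points of room for a 1-point criterion. Baseline can affect the chance of response but prevents none.
- A reader might infer that the precision is free. No gradient is documented. With odds ratios of 1 to 1.5 per level the gain ranges from slightly negative to under 1 point, and extra CMH strata cost power.
- A reader might infer bias. Over repeated randomisation the CMH comparison is valid, and its standard error allows for chance imbalance. What adjustment reduces is the error conditional on the imbalance that actually occurred.

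The contrast with the primary MMRM is suggestive only, since a continuous change score is tied to its baseline in a way that a responder indicator need not be. The replacement also brings some model dependence, such as a linear effect of the ordinal score and a sparse severe category.

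**Conclusion.** The point holds as a recommended improvement to efficiency and robustness. The key secondary test leaves out a baseline value that is already collected and probably prognostic, and this test decides whether the two lower doses are formally tested. Nothing in the plan is invalid, and the 91.7% stands.

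The size is modest: about 0 to +3.5 points of power at 66% versus 40% for odds ratios of 1 to 3 per level, and somewhat more for a smaller effect (about 3 to 6 points at 60% versus 40% with odds ratios of 2 and 3). The better argument is protection in the minority of trials with an unfavourable baseline split. These figures rest on the assumed baseline mix, gradient and TETRAS association, and on complete data without imputation.

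**What to change.** Before unblinding, specify a logistic model with treatment, the two stratification factors and baseline CGI-S (ordinal score) as main effects, fitted to the same imputed datasets. Report the standardised risk difference with a small-sample-corrected SE, pooled by MIANALYZE. The estimand, a difference in proportions, is unchanged. Use this as the main estimator with the CMH supportive; at minimum, add it as a pre-specified supportive analysis with the CMH kept as the main test. Do not add baseline CGI-S as further CMH strata.

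The cost is SAP text and one model, with no new data or participants. Making it the main estimator departs from Protocol 9.4.3.1, so it must be recorded in SAP 7.6, which lists changes to planned analyses. It adds mild model dependence. Null rejection was slightly above 5% with the uncorrected SE, and a corrected SE for the logistic estimator was not simulated here, so the chosen correction should be checked by simulation first.
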